## 8.3. Pharmacokinetic Analyses

#### 8.3.1. Overview of Planned Pharmacokinetic Analyses

The pharmacokinetic (PK) analyses will be based on the PK population, unless otherwise specified.

Table 8 provides an overview of the planned analyses, with full details being presented in Appendix 14: List of Data Displays. Summaries will be produced for week 12, week 24, and pooled.

 Table 8
 Overview of Planned Pharmacokinetic Analyses

Endpoints	Untransformed				Log-Transformed				
	Sum	Summary Individual		Summary		Individual			
	F	Т	F	L	F	Т	F	L	
Plasma Concentrations of GSK1278863	Y [1] [2]	Y	Y [1]	Y					
Derived PK Parameters	Y [3]	Y [3]	Y 	Y		Y[3]			
Dose Normalized PK Parameters	Y [3]	Y [3]	Y [3]	Y		Y [3]			

NOTES :

• T = Table, F = Figures, L = Listings, Y = Yes display generated.

Summary = Represents TFL related to any summaries (descriptive statistics) of the observed raw data.

• Individual = Represents FL related to any displays of individual subject observed raw data.

1. Linear and Semi-Log plots will be created on the same display.

2. Separate Mean (± SD) and Median plots will be generated.

3. Individual PK parameters calculated less than 4 time point concentration or any time deviated concentration will be omitted from summaries and figures.

#### 8.3.2. Drug Concentration Measures

Refer to Appendix 5: Data Display Standards & Handling Conventions (Section 10.5.3 Reporting Process & Standards).

Concentrations of GSK1278863 in plasma will be listed and summarized by dose group and nominal time. Individual plasma concentration-time profiles and median/mean profiles by dose group will be plotted. Each of figures will contain one plot on the untransformed scale (i.e. a linear plot) and one plot on the log transformed scale (i.e. a log-linear plot).
#### 8.3.3. Pharmacokinetic Parameters

#### 8.3.3.1. Deriving Pharmacokinetic Parameters

- Derivation of pharmacokinetic parameters will be performed by, or under the direct auspices of, Clinical Pharmacology & Science Promotion Office, GlaxoSmithKline K.K.
- Refer to Appendix 5: Data Display Standards & Handling Conventions (Section 10.5.3 Reporting Process & Standards).
- The pharmacokinetic parameters will be calculated by standard non-compartmental analysis according to current working practices and using Win Nonlin (version 6.3 or higher).
- All calculations of non-compartmental parameters will be based on actual sampling times.
- Pharmacokinetic parameters described in Table 9 will be determined from the Plasma GSK1278863 concentration-time data, as data permits.

Parameter	Parameter Description
AUC(0-4)	Area under the concentration-time curve from time zero to the time of the last quantifiable concentration (C(last)) will be calculated using the linear trapezoidal rule for each incremental trapezoid and the linear trapezoidal for each decremental trapezoid. The concentration at 0 hr will be set to 0.
AUC(0-7)	Area under the concentration-time curve from time zero to seven will be calculated using the linear trapezoidal rule for each incremental trapezoid and the linear trapezoidal for each decremental trapezoid. The concentration at 0 hr and 7 hr will be set to 0.
Cmax	Maximum observed concentration, determined directly from the concentration-time data.
Tmax	Time to first occurrence of Cmax will be obtained directly from the concentration-time data.
NOTES:	

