 - Screening: anytime after consenting and prior to first dose of study medication (Day 1)
 - Week 12: window from weeks 10-14 (inclusive)
 - End of study: window from weeks 20-24 (inclusive)
 - Early study medication discontinuation or study withdrawal: withdrawal eye exam as close to the last dose as possible. Re-conduct is not required if the exam is conducted within two weeks prior to withdrawal visit.
5. Only for females of reproductive potential.
6. Only at determination of menopausal status in female subjects (Section 5.1.).
7. See Table 7
8. For optional genetic research, informed consent should be obtained before the specimen collection.
9. See Section 7.4.1.
10. For examination at early withdrawal, the specified assessments should be performed as far as possible.
11. In the rescreening case, the previous result of ophthalmology exam at the screening may be used and the ophthalmology exam at the rescreening is not necessary, if the subject meets all of the following criteria and the investigator judges it appropriate.
 - There were no findings that would suggest a repeat ophthalmology exam performed within the next 3 months at the latest screening ophthalmology exam.
 - Subjects had no new eye-related symptoms or complaints since the latest screening ophthalmology exam until rescreening.
 - The latest screening ophthalmology exam was performed within 3 months prior to anticipated Day 1.
12. Exams should be conducted at least one week after ESA treatment.

Table 7 Blood Sampling Schedule for Pharmacokinetics

PK sample	Week 12 ²	Week 24 ²
Blood sampling timing ¹		1, 2, 3, and 4 h after administration of GSK1278863

Subjects must take the study medication in consideration of blood sampling time. Subjects will record the date and time of the last two study medication doses taken prior to blood sampling in the medication diary. Preferably, there should be an interval of at least 12 h between these two doses.

1. Blood sampling should be completed within +/- 30 min of the planned collected time.
2. Blood sampling not performed at this visit may be postponed until the following visits.

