9.4.3. Pharmacokinetic Analysis

For plasma concentrations of GSK1278863 over time, individual data will be listed, and summary statistics at each time point will be calculated by each dose level. For PK parameters (AUC 0-4 and Cmax), summary statistics will be calculated by each dose level, and scatter plots against the dose level will be generated.

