# 2. SUMMARY OF KEY PROTOCOL INFORMATION

## 2.1. Changes to the Protocol Defined Statistical Analysis Plan

No changes from the originally planned statistical analysis specified in the protocol amendment v04 (Dated: 19/Jul/2017) are present.

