#### Planned and Actual Time

Reporting Standard	s					
Reporting for tab	Departing for tables, figures and formal statistical analyses:					
Planned time	
 
Planned time relative to dosing will be used in figures summaries statistical analyses and
 
					
calculation of	calculation of any derived parameters, unless otherwise stated.					
For Individua	For Individual PK figures, the plot will use actual relative time.					

 
The impact of visit days on
 
	f any major deviation from the planned assessment times and/or scheduled the analyses and interpretation of the results will be assessed as appropriate.					
Reporting for Dat	ta Listings:					
Planned and     IDSL Statistic	actual time relative to study drug dosing will be shown in listings (Refer to cal Principle 5.05.1).					
Unscheduled	l or unplanned readings will be presented within the subject's listings.					

 
Scheduled vi
 
	sits outside the protocol defined time-windows (i.e. recorded as protocol					
deviations) w	ill be included in listings, figures, summaries and statistical analyses.					
Unscheduled Visits						
Unscheduled visit	ts will not be included in summary tables, unless otherwise specified.					

 
If unschedule
 
	ed visits are included in a summary, it will be provided how a summary will be					
produced as	appropriate.					
Unscheduled visit	ts will not be included in figures, unless otherwise specified.					
All unscheduled	visits will be included in listings.					
Descriptive Summa	ry Statistics					
Continuous Data	Refer to IDSL Statistical Principle 6.06.1: This does not apply to the output of statistical models or when the standard list is inappropriate.					
	• Hgb and iron summary statistics will include 95%CI and percentiles (P25 and P75).					
	• Dose level and dose adjustment frequency summary statistics will include mode.					
Categorical Data	N, n, frequency, %					
Reporting of Pharm	acokinetic Concentration Data					
Descriptive	Descriptive Refer to IDSL Statistical Principle 6.06.1					
Summary Statistics Assign zero to NQ values (Refer to GUI_51487 for further details)						
Reporting of Pharmacokinetic Parameters						
Descriptive N, n, geometric mean, 95% CI of geometric mean, standard deviatior						
Summary Statistics of log-transformed data and between geometric coefficient of variation (CV						
(Log Transformed)	(%)) will be reported.					

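### The parameter labelled AUC(0-4) ends at each subject's last actual sampling time, normally 3.5 to 4.5 h, instead of at 4.0 h; the supplementary AUC(0-7) rests on an assumed zero at 7 h

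*SAP*

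**What the plan says.** **Sampling.** Protocol Table 7 (Section 7.1) schedules PK samples at "1, 2, 3, and 4 h after administration of GSK1278863" at Weeks 12 and 24. There is no pre-dose sample and none after 4 h. The window is "Blood sampling should be completed within +/- 30 min of the planned collected time".

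**AUC(0-4).** SAP Table 9 defines it as the "Area under the concentration-time curve from time zero to the time of the last quantifiable concentration", by the linear trapezoidal rule with the 0 h value set to 0. SAP 8.3.3.1 adds: "All calculations of non-compartmental parameters will be based on actual sampling times". A note to Table 9 expects the last quantifiable concentration at 4 h but does not require it.

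**AUC(0-7).** This is a linear trapezoid to 7 h. "The concentration at 0 hr and 7 hr will be set to 0". SAP 10.6.5 repeats the rule. Neither place gives a reason.

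**Exclusions.** SAP Table 8 (note 3) and SAP 10.6.5 leave out of summaries and figures any profile with fewer than four concentrations or with a sample beyond ±30 min.

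**Protocol.** The endpoint table lists AUC and Cmax without an interval. Section 9.4.3 is specific: "For PK parameters (AUC 0-4 and Cmax), summary statistics will be calculated by each dose level". AUC(0-7) appears only in the SAP, while SAP 2.1 states: "No changes from the originally planned statistical analysis specified in the protocol amendment v04".

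**The concern.** A partial area can be compared between subjects only if everyone is integrated over the same interval. Under Table 9 the upper limit is whatever time the last quantifiable sample was drawn. Two subjects with identical concentration curves, sampled at 3.5 h and 4.5 h, both stay in the summaries and both receive a value called AUC(0-4), yet one area covers an hour more than the other. The clock difference then passes into the dose-level, dose-normalised and tablet-strength displays (SAP Tables 4.3-4.8, Figures 4.5-4.15). No population PK analysis is planned that would use the actual times differently (SAP 8.3.4).

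The AUC(0-7) rule raises a lesser question. The part after the last sample contains no measurement, so it is a fixed multiple of the last concentration however fast the subject eliminates the drug.

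**Working it through.** The documents state no AUC, half-life or absorption rate, so there is no plan figure to reproduce. The profiles below are assumptions, shown over a range.

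**Which time basis applies.** SAP 10.5.3 uses planned time for "any derived parameters, unless otherwise stated". SAP 8.3.3.1 does state otherwise, so actual times govern. A retained four-point profile therefore ends between 3.5 and 4.5 h. It would end earlier only if the last value were not quantifiable.

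**AUC(0-4): one profile in full.** Assumed one-compartment oral curve, scaled to unit dose/volume:

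C(t) = ka/(ka − k) × (e^(−kt) − e^(−ka·t)), with k = ln 2 / half-life.

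With ka = 1/h and half-life 4 h, C = 0.572, 0.692 and 0.659 at 1, 2 and 3 h, then 0.623 at 3.5 h, 0.583 at 4 h and 0.541 at 4.5 h.

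- Area 0-3 h: 0.286 + 0.632 + 0.675 = 1.593
- Last sample 3.5 h: 1.593 + 0.25 × (0.659 + 0.623) = 1.914
- Last sample 4.0 h: 1.593 + 0.50 × (0.659 + 0.583) = 2.214
- Last sample 4.5 h: 1.593 + 0.75 × (0.659 + 0.541) = 2.493

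Relative to 4.0 h: 1.914/2.214 = −13.6%; 2.493/2.214 = +12.6%.

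**AUC(0-4): the range**, relative to the same profile sampled at 4.0 h:

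| Half-life | ka (/h) | 3.5 h | 3.75 h | 4.25 h | 4.5 h |
|---|---|---|---|---|---|
| 1 h | 1 | −7.7% | −3.6% | +3.3% | +6.3% |
| 1 h | 2 | −5.3% | −2.5% | +2.3% | +4.3% |
| 2 h | 1 | −11.1% | −5.4% | +5.0% | +9.7% |
| 2 h | 2 | −9.1% | −4.4% | +4.1% | +7.9% |
| 4 h | 1 | −13.6% | −6.7% | +6.4% | +12.6% |
| 4 h | 2 | −11.7% | −5.7% | +5.5% | +10.8% |

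If a 1 h absorption lag is also assumed (ka 1/h, half-life 4 h), the edges widen to about −21% and +20%.

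**AUC(0-4) after the fix.** Log-linear interpolation or extrapolation to exactly 4.0 h, from the 3 h and last samples, brings every profile in the table within about 0.15% of its 4.0 h value. With the lag it is within about 0.6%.

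**AUC(0-7): the tail.** The added triangle is (7 − t_last)/2 × C(last). That is 1.75, 1.5 or 1.25 × C(last) for a last sample at 3.5, 4.0 or 4.5 h. For a 4.0 h sample, compare 1.5 × C4 with exponential decay after 4 h, C4 × (1 − e^(−3k))/k. The effect on the total is (AUC to 4 h + 1.5 × C4) / (AUC to 4 h + exponential tail) − 1.

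| Half-life | Exponential tail | 4-7 h slice alone | Total AUC(0-7), ka 1/h | Total AUC(0-7), ka 2/h |
|---|---|---|---|---|
| 0.5 h | 0.710 × C4 | +111% | +4.7% | +1.6% |
| 1 h | 1.262 × C4 | +19% | +2.6% | +1.8% |
| 2 h | 1.865 × C4 | −20% | −5.4% | −4.6% |
| 4 h | 2.339 × C4 | −36% | −13.7% | −12.3% |

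Example (ka 1/h, half-life 4 h): (2.214 + 0.874)/(2.214 + 1.363) = 3.088/3.577 = −13.7%. The triangle and the exponential tail agree at a half-life of about 1.3 h.

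**Does the tail still carry elimination?** With ka 1/h, C4 is 0.144 at half-life 1 h and 0.583 at 4 h. The planned tails are 0.216 and 0.874, a 4.0-fold difference. The exponential tails are 0.182 and 1.363, a 7.5-fold difference. The contrast is compressed but present.

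**The case against.** Several points on the other side stand. The AUC(0-4) percentages are for the window edges: at 15 minutes off, the assumed profiles give about −7% to +6%, and at 4.0 h nothing. The ±30 min exclusion bounds the effect. PK is secondary and descriptive with no hypothesis test, and the primary Hgb analysis, Cmax and the concentration displays do not use AUC.

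On AUC(0-7), a reader might infer that the reported value is wrong by up to +111%, or that differences in elimination are erased. The documents support neither. The +111% concerns only the 4-7 h slice at a half-life of 0.5 h, where little drug remains, and it moves the total by 2-5%. The last concentration is measured and reflects each subject's elimination. With no half-life given, even the direction of the error is unknown.

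A reader might also infer that the SAP replaced the protocol's AUC without saying so. It did not. AUC(0-4) is kept, AUC(0-7) is added beside it and is pre-specified in two places, Table 9 allows additional parameters, and protocol Section 9 defers analysis detail to the RAP. What remains is minor: SAP 2.1 does not mention the addition.

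None of this gives AUC(0-4) a fixed end point. The expectation that the last quantifiable value falls at 4 h does not standardise the interval.

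**Conclusion.** The concern holds for AUC(0-4), which is the main point. Its label promises a fixed interval and its definition does not. The end point normally varies over 3.5-4.5 h, which changes a value by about −5% to −14% at the early edge and +4% to +13% at the late edge. Those ranges assume a one-compartment profile without lag, ka 1-2/h and half-life 1-4 h. The effect is sampling-clock variability added to a secondary descriptive endpoint. It is not a systematic shift, unless samples happen to be consistently early or late, which the documents do not suggest.

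The AUC(0-7) point is subsidiary. The assumed zero compresses differences in elimination and changes the total by roughly +5% to −14% over assumed half-lives of 0.5-4 h, on the further assumption of exponential decay after 4 h. Its sign cannot be determined from the documents.

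**What to change.** 1. In SAP Table 9, define AUC(0-4) as the partial area from 0 to exactly 4.0 h. Keep actual sampling times, and obtain the 4.0 h concentration by log-linear interpolation (last sample after 4.0 h) or extrapolation (last sample before 4.0 h). State what is done when the 4 h value is not quantifiable. Name this as the AUC for the protocol endpoint, in line with protocol 9.4.3.
2. Drop AUC(0-7). Alternatively, keep it as supplementary, labelled in every display as resting on an assumed zero at 7 h, and list it in SAP 2.1 as an addition to the protocol.

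Replacing the zero with a subject-specific log-linear tail is less attractive. The slope would rest on very few points up to 4 h, and on assumed profiles with a 1 h half-life it changed the error in AUC(0-7) little.

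**Cost.** SAP wording and a setting in the non-compartmental software, with no new data. AUC(0-7) is lost or demoted. AUC(0-4) gains a short interpolation or extrapolation step of at most half an hour for samples within the window.

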#### Table 9 Derived Pharmacokinetic Parameters

• Additional parameters may be included as required.

• C(last) is expected to be the concentration observed at 4hours after the most recent dose.

#### 8.3.4. Population Pharmacokinetic (PopPK) Analyses

No population pharmacokinetic analysis is planned.

# 8.4. Pharmacodynamic Analyses

No pharmacodynamic analysis is planned.

# 8.5. Pharmacokinetic / Pharmacodynamic Analyses

No pharmacokinetic / pharmacodynamic analysis is planned.

#### 204716

# 10. APPENDICES

Section	Appendix
RAP Section 4	: Analysis Populations
Section 10.1	Appendix 1: Protocol Deviation Management and Definitions for Per Protocol Population
RAP Section 5	: General Considerations for Data Analyses & Data Handling Conventions
Section 10.2	Appendix 2: Time and Events
Section 10.3	Appendix 3: Assessment Windows
Section 10.4	Appendix 4: Treatment States & Phases
Section 10.5	Appendix 5: Data Display Standards & Handling Conventions
	Study Treatment & Sub-group Display Descriptors
	Baseline Definitions & Derivations
	Reporting Process & Standards
Section 10.6	Appendix 6: Derived and Transformed Data
	General, Study Population & Safety
	Efficacy
	Pharmacokinetic
Section 10.7	Appendix 7: Premature Withdrawals & Handling of Missing Data
	Premature Withdrawals
	Handling of Missing Data
Section 10.8	Appendix 8: Values of Potential Clinical Importance
Section 10.9	Appendix 9: Multicenter Studies
	Laboratory Values
	• ECG
	Vital Signs
Section 10.10	Appendix 10: Examination of Covariates and Subgroups
Section 10.11	Appendix 11: Multiple Comparisons and Multiplicity
Section 10.12	Appendix 12: Model Checking and Diagnostics for Statistical Analyses
Other RAP App	endices
Section 10.13	Appendix 13: Abbreviations & Trade Marks
Section 10.14	Appendix 14: List of Data Displays
Section 10.15	Appendix 15: Example Mock Shells for Data Displays

# 10.1. Appendix 1: Protocol Deviation Management and Definitions for Per Protocol Population

Per Protocol Population will not be defined in this study.

204716

# 10.2. Appendix 2: Time & Events

#### 10.2.1. Protocol Defined Time & Events

Period	Scre	eening				Trea	tment				Follow-up
Visits All assessments pre-dialysis, unless noted.		Week -4	Day 1	Week 4	Week 8	Week 12	Week 16	Week 20	Week 24	Early withdraw al 	2–4 weeks after Week 24 or early withdrawal
Allowable window (days)		±7	-	±3	±3	±3	±3	±3	±3	-	±3
Informed consent	Х				-			-			
Inclusion/exclusion		X	Х								
Medical history, demography, height, body weight 		Х									
IWRS call		X	Х	Х	Х	Х	Х	X	Х	Х	Х
Study medication dispensing 			Х	Х	Х	Х	Х	Х			
Study medication compliance				Х	Х	Х	Х	Х	Х	Х	
Vital signs (before and after dialysis) 		X	Х	Х		Х			Х	Х	Х
Ophthalmology examination 		X 			•	$\leftrightarrow$		← →		<->	
ECG		X				X			Х		
HemoCue Hgb			Х	Х	Х	Х	Х	Х	Х		
Hematology		X 	Х	Х	Hgb only	Х	Hgb only	Hgb only	Х	х	Х
Clinical chemistry		Х	Х	X		Х			Х	Х	Х
Ferritin, TSAT		X	Х	Х		Х			Х	Х	
Serum iron, TIBC, UIBC, serum transferrin, hepcidin			Х	Х		Х			Х	X	
Serum pregnancy test 		X	Х	X		X			Х	Х	Х
Estradiol  , FSH 		X									
Pharmacokinetics 						Х			Х		
iPTH			Х	Х		Х			Х		
Genetics sample 			X								
Adverse event assessment 							$\rightarrow$				
Concomitant medication assessment		◀───									

#### 204716

- 1. Body weight is measured after dialysis.
- 2. If a subject visit the study site only to receive study medication, only the IWRS call, study medication dispensing, and study medication compliance will be required
- 3. At visits without dialysis, only one measurement of each parameter will be obtained.
- 4. Ophthalmology exams should be conducted at the following time points.
  - Screening: anytime after consenting and prior to first dose of study medication (Day 1)
  - Week 12: window from weeks 10-14 (inclusive)
  - End of study: window from weeks 20-24 (inclusive)
  - Early study medication discontinuation or study withdrawal: withdrawal eye exam as close to the last dose as possible. Re-conduct is not required if the exam is conducted within two weeks prior to withdrawal visit.
- 5. Only for females of reproductive potential.
- 6. Only at determination of menopausal status in female subjects (Section 5.1).
- 7. See Table 7
- 8. For optional genetic research, informed consent should be obtained before the specimen collection.
- 9. See Section 7.4.1.
- 10. For examination at early withdrawal, the specified assessments should be performed as far as possible
- 11. The previous result of ophthalmology exam at the screening may be used if the subject meets all of the following criteria and the investigator judges it appropriate.
  - There were no findings that would suggest a repeat ophthalmology exam performed within the next 3 months at the latest screening ophthalmology exam.
  - Subjects had no new eye-related symptoms or complaints since the latest screening ophthalmology exam.
  - The latest screening ophthalmology exam was performed within 3 months prior to anticipated Day 1.
- 12. Exam should be conducted at least one week after ESA treatment.

#### • Blood Sampling Schedule for Pharmacokinetics

PK sample	Week 12 	Week 24 
Blood sampling timing 	1, 2, 3, and 4 h after a	administration of GSK1278863

Subjects must take the study medication in consideration of blood sampling time. Subjects will record the date and time of the last two study medication doses taken prior to blood sampling in the medication diary. Preferably, there should be an interval of at least 12 h between these two doses.

1. Blood sampling should be completed within +/- 30 min of the planned collected time.

2. Blood sampling not performed at this visit may be postponed until the following visits.

#### 10.3. Appendix 3: Assessment Windows

All data will be reported according to the nominal visit date for which it was reported (that is, no visit windows will be applied during dataset creation). Permissible range at each visit was specified in time & event table (See Appendix 2). Records in the eCRF unscheduled visit will not be slotted to a particular time point, but remain as unscheduled if they are either summarized or listed unless otherwise specified.

#### 10.3.1. Definitions of Analysis Time Point

Analysis Time Point	Definitions
Screening [1]	Data collected in Screening visit
Day 1 [1]	Data collected in Day 1 visit
Week 4	Data collected in Week 4 visit
Week 8	Data collected in Week 8 visit
Week 12	Data collected in Week 12 visit
Week 16	Data collected in Week 16 visit
Week 20	Data collected in Week 20 visit
Week 24	Data collected in Week 24 visit
Follow-up	Data collected in Follow-up visit

Note: Any unscheduled visit will not be slotted to a particular time point.

[1] For rescreened subjects, data collected in screening-pass visit will be used for analysis. They may have multiple records at Screening and/or Day 1 visit, which associates with a screening-pass visit and screening failure visit(s)

